Secondary/exploratory endpoints include the proportion with undetectable viral loads at week 48, proportion with emergent drug resistance, change in CD4 counts, and evaluation retention in care. Substance use throughout the study will be evaluated by the NIDA Modified-ASSIST questionnaire. Adherence will be evaluated by refill history/percentage of days covered, ACTG Self-Report Adherence questionnaire, and FTC-TP and TDF-DP levels by dried blood spots.

Follow-up:

Participants will be followed up at weeks 6, 12, 24, 36, and 48. Participants will be compensated for visits completed at \$20 per hour.

Brief Description: Illicit substance use in the United States is a growing concern across all states. Use of illicit drugs such as cocaine, heroin, methamphetamine, prescription opioids and stimulants, and 3,4-methylenedioxy-methamphetamine (Ecstasy, MDMA) among others, has remained steady in many parts of the United States [1]. In 2017, 6% of new HIV infections occurred in people who injected drugs and 3% were in gay/bisexual men who injected drugs [2]. Furthermore, injection of illicit drugs has been linked to outbreaks of HIV and viral hepatitis acquisition [3].

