After obtaining written informed consent, prospective participants will be screened with a clinical assessment (physical exam), laboratory testing (CBC, CMET, HBV/HCV serology, CD4, HIV RNA), and substance use evaluation (NIDA ASSIST) to evaluate study eligibility. Eligible patients may initiate treatment with B/F/TAF on the same day as the screening visit or start within 30 days of screening.

Post-entry evaluations will occur at weeks 6, 12 and 24, 36, and 48. Clinical and safety laboratory monitoring including blood chemistries, plasma HIV RNA levels, CD4 counts and blood sampling for ART drug quantification will take place at week 6, 24, and 48 weeks. Pregnancy testing will be performed any time pregnancy is suspected. Assessment of adverse events, adherence, ongoing substance use, and quality of life will be assessed at each visit. Adherence measures include pill counts, self-reported by visual analog scale by the ACTG Brief Adherence Self Report [17] and pharmacokinetic sampling (see below). Ongoing illicit substance use will be evaluated quarterly at week 12, 24, 36, and 48 through the NIDA ASSIST [18]. Referral for substance use counseling and/or outpatient or inpatient treatment will be offered. Additionally, the Short Form 12 survey will be utilized to evaluate quality of life and patient reported outcomes [19-21]. See schedule of events table for detail.

Virologic Failure:

Suspected virologic failure will be defined as plasma HIV RNA > 400 copies/mL after week 12 and will be confirmed by a repeat measurement within 28 days. Participants with confirmed virologic failure will undergo genotype resistance testing using the Genosure Prime assay. Participants with emergent INI or TAF related HIV drug resistance development will undergo ART revision but will continue to be followed on study.

Adverse Events:

Signs and symptoms will be graded according to the DAIDS Table for Grading the Severity of Adult and Pediatric Adverse Events [22]. All signs and symptoms grade 3 or above or any grade that led to treatment discontinuation, will be recorded on study case report forms and tracked in the REDCap data management

Pharmacokinetic Sampling:

Blood for PK studies will be collected at three time points while on study, week 6, 24 and 48. 4mL of K2 EDTA whole blood will be collected via venipuncture for tenofovir-diphosphate (TDF-DP) and

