Race	X					
Ethnicity	X					
Education	X					
Gender	X					
ART Exp	X					
Housing	X					
Income	X					
Reported Illicit Substance or UDS Result	X					
Baseline/Archived Resistance	X					
Clinical Information						
CBC	X			X		X
Creatinine	X	X		X		X
AST	X	X		X		X
ALT	X	X		X		X
HBV c Ab	X					
HBV s Ab	X					
HBV s Ag	X					
HCV Ab	X					
HIV RNA	X	X		X		X
CD4	X			X		X
CD4%	X			X		X
CD4/CD8	X			X		X
Pregnancy (if applicable)	X	X	X	X	X	X
Emergent Resistance		X		X		X
Safety/AE Assessment						
Physical Exam						
	X			X		X

Questionnaire						
ACTG Adherence		X	X	X	X	X
NIDA ASSIST	X		X	X	X	X
SF-12 Survey	X			X		X
Lab Collection						
DBS Card Collection		X		X		X

Addendum B: Adherence Questionnaire – adapted from ACTG Visual Analog Scale

BASE Study: ACTG Adherence

Name:

Visit Week:

DOB:

Participant ID:

Reported Adherence

[figure not shown]
We understand that many people on anti-HIV medications find it very difficult to take them regularly. We would like to know HOW MUCH of your anti-HIV medications you have taken DURING THE LAST MONTH.

Please put a cross (**X**) on the line below at the point showing your best guess about how much of your anti-HIV medication you have taken **in the last month**. We would be surprised if this was 100% for most people.

For example: **0%** means you have taken **none** of your anti-HIV medication.

50% means you have taken **half** your anti-HIV medication.

100% means that you have taken **every single dose** of your anti-HIV medication in the past month.

Self-reported adherence score: _____

Addendum C: Substance Use Questionnaire – adapted from NIDA-ASSIST

BASE Study: NIDA ASSIST

Name: _____ Visit Week: _____
DOB: _____ Participant ID: _____

NIDA Quick Screen:

In the past year, how often have you used the following?

Alcohol	Never	Once or twice	Monthly	Weekly	Daily or Almost Daily
• Men (≥ 5 drinks/day)					
• Women (≥ 4 drinks/day)					
Tobacco Products					
Prescription Drugs for Non-Medical Reasons					
Illegal Drugs					

NIDA Modified Screen:

1. In your lifetime, which of the following substances have you ever used?

Cannabis (marijuana, pot, grass, hash, CBD, etc.)	Yes	No
Cocaine (coke, crack, etc.)		
Prescription stimulants (Ritalin, Concerta, Dexedrine, Adderall, diet pills, etc)		
Methamphetamine (speed, crystal meth, Tina, ice, etc)		
Inhalants (nitrous oxide, glue, gas, paint thinner, "poppers", etc.)		

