Sedatives or sleeping pills (Valium, Ativan, Xanax, Librium, Rohypnol, GHB, etc)		
Hallucinogens (LSD, acid, mushrooms, PCP, Special K, ecstasy, etc)		
Street opioids (heroin, opium, etc)		
Prescription opioids (fentanyl, oxycodone [Oxycontin, Percocet], methadone, Buprenorphine, oxymorphone, hydrocodone [Vicodin])		
Other – specify:		

2. In the past 3 months, how often have you used the substances you mentioned (first drug, second drug, etc)?

Frequency (Points listed in box)	Never	Once/Twice	Monthly	Weekly	Daily or Almost Daily
Cannabis (marijuana, pot, grass, hash, CBD, etc.)	0	2	3	4	6
Cocaine (coke, crack, etc.)	0	2	3	4	6
Prescription stimulants (Ritalin, Concerta, Dexedrine, Adderall, diet pills, etc)	0	2	3	4	6
Methamphetamine (speed, crystal meth, Tina, ice, etc)	0	2	3	4	6
Inhalants (nitrous oxide, glue, gas, paint thinner, "poppers", etc.)	0	2	3	4	6
Sedatives or sleeping pills (Valium, Ativan, Xanax, Librium, Rohypnol, GHB, etc)	0	2	3	4	6
Hallucinogens (LSD, acid, mushrooms, PCP, Special K, ecstasy, etc)	0	2	3	4	6
Street opioids (heroin, opium, etc)	0	2	3	4	6
Prescription opioids (fentanyl, oxycodone [Oxycontin, Percocet], methadone, Buprenorphine, oxymorphone, hydrocodone [Vicodin])	0	2	3	4	6
Other – specify:	0	2	3	4	6

3. In the past 3 months, how often have you a strong desire or urge to use (first drug, second drug, etc)?

Frequency (Points listed in box)	Never	Once/Twice	Monthly	Weekly	Daily or Almost Daily
Cannabis (marijuana, pot, grass, hash, CBD, etc.)	0	3	4	5	6
Cocaine (coke, crack, etc.)	0	3	4	5	6
Prescription stimulants (Ritalin, Concerta, Dexedrine, Adderall, diet pills, etc)	0	3	4	5	6
Methamphetamine (speed, crystal meth, Tina, ice, etc)	0	3	4	5	6
Inhalants (nitrous oxide, glue, gas, paint thinner, "poppers", etc.)	0	3	4	5	6

Sedatives or sleeping pills (Valium, Ativan, Xanax, Librium, Rohypnol, GHB, etc)	0	3	4	5	6
Hallucinogens (LSD, acid, mushrooms, PCP, Special K, ecstasy, etc)	0	3	4	5	6
Street opioids (heroin, opium, etc)	0	3	4	5	6
Prescription opioids (fentanyl, oxycodone [Oxycontin, Percocet], methadone, Buprenorphine, oxymorphone, hydrocodone [Vicodin])	0	3	4	5	6
Other – specify:	0	3	4	5	6

4. In the past 3 months, how often has your use (first drug, second drug, etc) lead to health, social, legal or financial problems?

Frequency (Points listed in box)	Never	Once/Twice	Monthly	Weekly	Daily or Almost Daily
Cannabis (marijuana, pot, grass, hash, CBD, etc.)	0	4	5	6	7
Cocaine (coke, crack, etc.)	0	4	5	6	7

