7. Have you ever tried and failed to control, cut down or stop using (first drug, second drug, etc)?

Frequency (Points listed in box)	No, never	Yes, but not in the past 3 months	Yes, in the past 3 months
Cannabis (marijuana, pot, grass, hash, CBD, etc.)	0	3	6
Cocaine (coke, crack, etc.)	0	3	6
Prescription stimulants (Ritalin, Concerta, Dexedrine, Adderall, diet pills, etc)	0	3	6
Methamphetamine (speed, crystal meth, Tina, ice, etc)	0	3	6
Inhalants (nitrous oxide, glue, gas, paint thinner, "poppers", etc.)	0	3	6
Sedatives or sleeping pills (Valium, Ativan, Xanax, Librium, Rohypnol, GHB, etc)	0	3	6
Hallucinogens (LSD, acid, mushrooms, PCP, Special K, ecstasy, etc)	0	3	6
Street opioids (heroin, opium, etc)	0	3	6
Prescription opioids (fentanyl, oxycodone [Oxycontin, Percocet], methadone, Buprenorphine, oxymorphone, hydrocodone [Vicodin])	0	3	6
Other – specify:	0	3	6

8. Have you ever used any drug by injection (non-medical use only)?

- No, never
- Yes, but no in the past 3 months
- Yes, in the past 3 months

9. Substance use grading

Substance Involvement Score	Total (SI Score)	Risk Level
Cannabis (marijuana, pot, grass, hash, CBD, etc.)		
Cocaine (coke, crack, etc.)		
Prescription stimulants (Ritalin, Concerta, Dexedrine, Adderall, diet pills, etc)		
Methamphetamine (speed, crystal meth, Tina, ice, etc)		
Inhalants (nitrous oxide, glue, gas, paint thinner, "poppers", etc.)		
Sedatives or sleeping pills (Valium, Ativan, Xanax, Librium, Rohypnol, GHB, etc)		
Hallucinogens (LSD, acid, mushrooms, PCP, Special K, ecstasy, etc)		
Street opioids (heroin, opium, etc)		
Prescription opioids (fentanyl, oxycodone [Oxycontin, Percocet], methadone, Buprenorphine, oxymorphone, hydrocodone [Vicodin])		
Other – specify:		

SI risk Level

Level of risk associate with SI score for Illicit or nonmedical prescription drug use	
0-3	Lower Risk
4-26	Moderate Risk
27+	High Risk

Addendum D: Patient Reported Outcomes – adapted from SF-12

BASE Study: SF-12

Name:

Visit Week:

DOB:

Participant ID:

1. In general would you say your health is:
 Excellent
 Very good
 Good
 Fair
 Poor
2. The following questions are about activities you might do during a typical day. Does your health now limit you in these activities? If so, how much?

Moderate activities, such as moving a table, pushing a vacuum cleaner, bowling, or playing golf:

Yes, limited a lot
 Yes, limited a little
 No, not limited at all

Climbing several flights of stairs:

Yes, limited a lot
 Yes, limited a little

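### Addendum C's scored drug-use items are not limited to non-medical use, so methadone or buprenorphine taken only as prescribed can score as moderate-risk illicit use

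*Combined protocol and SAP*

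**What the plan says.** The Abstract gives the form its job: "Substance use throughout the study will be evaluated by the NIDA Modified-ASSIST questionnaire". Methods sets it at weeks 12, 24, 36 and 48 as the measure of ongoing illicit use. The same section adds: "Referral for substance use counseling and/or outpatient or inpatient treatment will be offered".

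In Addendum C, item 1 is an unscored yes/no list: "In your lifetime, which of the following substances have you ever used". Item 2 is the first scored item: "In the past 3 months, how often have you used the substances you mentioned". Items 3 to 7 score urges, resulting problems, failed obligations, concern from others, and failed attempts to cut down. All of them use the same substance rows, and the opioid row is "Prescription opioids (fentanyl, oxycodone [Oxycontin, Percocet], methadone, Buprenorphine, oxymorphone, hydrocodone [Vicodin". Item 9 totals each row separately and reads the total against a table titled "Level of risk associate with SI score for Illicit or nonmedical prescription drug use", with bands 0-3 (lower), 4-26 (moderate) and 27 or more (high).

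A non-medical limit appears in three places, none of which carries points: one Quick Screen row on prescription drugs, item 8 on injection, and the title of the risk table. The inclusion criteria count prescription drugs only when their use is inappropriate.

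**The concern.** The score's label and its items measure different things. The label and the eligibility criteria concern illicit or inappropriate use. The items ask about any use, and the opioid row names two drugs that are also prescribed to treat opioid dependence. Item 8 shows that the limit was written in where it was wanted, yet no scored item has it. A participant or interviewer who follows the printed form would record prescribed treatment as opioid use.

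This matters because the form cannot be checked against anything else scheduled. Addendum A records reported substance or urine drug screen result at baseline only. Neither Addendum A nor the Study Follow-up/Labs table has a row for substance-use treatment received. Addendum E says that some participants reduced or stopped their use after enrolment. If such a change comes with medication, the prescription-opioid row can move the wrong way, and treatment that might bear on adherence is not recorded in the schedule.

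**Working it through.** The documents give no figure to reproduce on this point. The check applies Addendum C's own points to one row.

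**Inputs (Addendum C)**
- Item 2: never 0, once/twice 2, monthly 3, weekly 4, daily or almost daily 6.
- Items 6 and 7: never 0, yes but not in the past 3 months 3, yes in the past 3 months 6.
- Bands: 0-3 lower, 4-26 moderate, 27+ high.

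**Formula.** For a person who takes the drug only as prescribed, let *q* be the item 2 points and *r* the total of items 3 to 7 on that row. Treat *r* as unchanged by the limit. The printed form gives *q* + *r*. With a non-medical limit, item 2 becomes never and the row gives *r*.

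| Frequency as prescribed | *r* = 0: printed / limited | *r* = 3: printed / limited | *r* = 6: printed / limited |
|---|---|---|---|
| Daily (6) | 6 moderate / 0 lower | 9 moderate / 3 lower | 12 moderate / 6 moderate |
| Weekly (4) | 4 moderate / 0 lower | 7 moderate / 3 lower | 10 moderate / 6 moderate |
| Monthly (3) | 3 lower / 0 lower | 6 moderate / 3 lower | 9 moderate / 6 moderate |
| Once/twice (2) | 2 lower / 0 lower | 5 moderate / 3 lower | 8 moderate / 6 moderate |

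**Reading the table**
1. The clean case is daily use with *r* = 0: 6 against 0, which crosses from lower to moderate.
2. The lower/moderate boundary is crossed only when *r* is 3 or less. With past-only answers to both items 6 and 7 (*r* = 3 + 3 = 6), the total is 12 as printed and 6 as limited. The score is too high by 6, but the band is the same.
3. Daily use with the maximum on items 6 and 7 gives 6 + 6 + 6 = 18. Adding a daily urge on item 3 gives 24. Both stay below 27, so with never on items 4 and 5 the row does not reach the high band.

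**Which rows.** The prescription stimulant and sedative rows also name prescribed medicines under the same unlimited stems, so the same arithmetic applies. Totals are kept by row, so the street-opioid, cocaine and methamphetamine rows do not change.

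**Which results.** The primary endpoint is HIV RNA below 50 copies/mL at week 24 and does not use the form. The Data analysis section plans no analysis of the score. Exploratory endpoint 3b adjusts week-48 suppression by type of illicit substance without naming the source of that variable. It could come from this form or from the baseline row in Addendum A.

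**The case against.** The strongest reply is that the form's purpose is clear. Methods calls it a measure of illicit use, the risk table is titled for non-medical use, and a Quick Screen row asks about non-medical use of prescription drugs. An interviewer could apply that limit unprompted, and the cited source questionnaire may have administration instructions that cannot be seen here. This part stands: the score *can* be wrong, not *must* be. It does not remove the gap, because the printed addendum states no such rule and unwritten discretion is itself a source of inconsistent measurement. The Quick Screen row is only a partial cross-check. It is unscored, names no drug class, has no stated link to items 1 to 7, and covers the past year, which at the nominal visit weeks reaches back before entry.

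A reader might infer more than the documents support:
- *That the trial refers participants to the very treatment it then scores as use.* The referral is generic and names no medication. Such treatment may follow a referral.
- *That participants who improve are classified as continuing users overall.* Someone who moves from heroin to prescribed buprenorphine still answers never on item 2 of the street-opioid row. Only the prescription-opioid row is wrong.
- *That the information is lost for good.* It cannot be recovered from the scheduled study data. Clinic records may help, and the Addendum E interviews, planned for 20 to 25 participants near week 48, ask about help received for substance use.
- *That a number misclassified can be given.* The documents hold no figure for use of these medicines in this population.

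It is also fair to say that rewording during the study mixes two versions of the score within participants. That is a real cost.

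**Conclusion.** The mismatch between the items and the label is real and can be checked on the page. For daily use only as prescribed, with never on items 3 to 7, the error is 6 points on one row, enough to move it from lower to moderate risk. This assumes that the form is followed as printed and that no separate instruction limits it.

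The reach is modest. It covers the description of ongoing illicit use at weeks 12 to 48 and possibly exploratory endpoint 3b. The primary result is untouched, and no analysis specified under Data analysis uses the score. The number of participants affected cannot be derived from the documents. The correction is worth making because it is cheap and this is the only instrument scheduled for follow-up drug use.

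**What to change.** 1. In Addendum C, items 1 to 7, add an instruction that the prescription rows (opioids, stimulants, sedatives) count only use for non-medical reasons or other than as prescribed.
2. Add one unscored yes/no line for methadone or buprenorphine taken as prescribed.
3. In Addendum A, add one row at weeks 12, 24, 36 and 48 for substance-use treatment received (type and dates), reported descriptively.
4. State the source of the substance-type variable in exploratory endpoint 3b.

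Do not add a table of week-24 suppression by treatment received. It would be a post-baseline subgroup with little precision: for illustration, 4 suppressed of 5 has an exact 95% interval of about 0.28 to 0.99.

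The cost is a form revision and two short data fields at visits that already take place. The downside is that scores before and after the change rest on different wording. Addendum E reports that some participants had already reached week 24, so completed forms should be flagged with the version used and, where clinic records allow, with prescribed use.
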